### Study Drug Interruption

LUM/IVA administration must be interrupted immediately, and the Vertex medical monitor or designee must be notified if any of the following criteria is met:

- ALT or AST  $> 8 \times ULN$
- ALT or AST  $\geq$ 5 × ULN for more than 2 weeks
- ALT or AST  $\ge 3 \times \text{ULN}$  in association with total bilirubin  $\ge 2 \times \text{ULN}$  and/or clinical jaundice

A thorough investigation of potential causes should be conducted, and the subject should be followed closely for clinical progression.

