#### 13.1.1.2 Clinically Significant Assessments

Study assessments including laboratory tests, ECGs, PEs, and vital signs will be assessed and those deemed to have clinically significant worsening from baseline will be documented as an AE. When possible, a clinical diagnosis for the study assessment will be provided, rather than the abnormal test result alone (e.g., urinary tract infection, anemia). In the absence of a diagnosis, the abnormal study assessment itself will be listed as the AE (e.g., bacteria in urine or decreased hemoglobin).

An abnormal study assessment is considered clinically significant if the subject has 1 or more of the following:

- Concomitant signs or symptoms related to the abnormal study assessment
- Further diagnostic testing or medical/surgical intervention
- A change in the dose of study drug or discontinuation from the study

Repeat testing to determine whether the result is abnormal, in the absence of any of the above criteria, does not necessarily meet clinically significant criteria. The determination of whether the study assessment results are clinically significant will be made by the investigator.

A laboratory value that is Grade 4 will not automatically be an SAE. A Grade 4 laboratory value will be an SAE if the subject's clinical status indicates a life-threatening AE.

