## 13.1.1.3 Documentation of Adverse Events

All AEs will be collected from the time the ICF is signed until the following times:

- For subjects who do not enroll: until time of screen failure (e.g., screen failure, withdrawal of consent)
- For enrolled subjects who have a Safety Follow-up Visit: through the Safety Follow-up Visit, with the exception of ocular AEs noted during the Follow-up OE.

- For enrolled subjects who do not have a Safety Follow-up Visit, the earliest of
  - o 14 days after the last dose of study drug, or
  - o the ETT Visit, if that visit is >10 days following the last dose of study drug (see Section 9.1.4)

All subject's parents or legal guardians will be queried, using nonleading questions, about the occurrence of AEs at each study visit. When possible, a constellation of signs and/or symptoms will be identified as 1 overall event or diagnosis. All AEs for enrolled subjects will be recorded in the CRF and source document. AEs for subjects who are screened but not subsequently enrolled will be recorded only in the subject's source documents. The following data will be documented for each AE:

- Description of the event
- Classification of "serious" or "nonserious"
- Date of first occurrence and date of resolution (if applicable)
- Severity
- Causal relationship to study drug(s)
- Action taken
- Outcome
- Concomitant medication or other treatment given

For the purposes of study analysis, if the event has not resolved at the end of the study reporting period (the Safety Follow-up Visit), it will be documented as ongoing. For purposes of regulatory safety monitoring, the investigator is required to follow the AE to symptom resolution or until the condition stabilizes.

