Additional summary table in which the frequency counts and percentages will be presented for TEAEs during the TE period for the following:

- All TEAEs by PT
- Non-Serious TEAEs by SOC and PT
- Related Non-Serious TEAEs by SOC and PT

In addition, listings containing individual subject data for all TEAEs leading to treatment interruption, TEAEs leading to treatment discontinuation, deaths, and serious adverse events (SAEs) will be provided separately for the TE Period. All AEs, including pre- and post-treatment AEs, will be presented in individual subject data listings for the TE Period.

Note that if an event increases in its severity, it will be reported as a separate event in the clinical database and thus may be counted more than once.

Analysis of AEs of Special Interest (AESI):

Three types of AESIs are proposed for Study 124; the Customized MedDRA Queries (CMQ) used may change before database lock.

1. Elevated Transaminases AESI

The AESI of elevated transaminases is defined as AEs whose PTs fall into any of the following categories:

- Alanine aminotransferase abnormal
- Alanine aminotransferase increased
- Aspartate aminotransferase abnormal
- Aspartate aminotransferase increased
- Transaminases abnormal
- Transaminases increased
- Liver function test abnormal
- Liver function test increased
- Hypertransaminasaemia
- Hepatic enzyme increased
- Hepatic enzyme abnormal
- 2. Respiratory Symptom AESI

The AESI of respiratory symptoms is defined as AEs whose PTs fall into any of the following categories:

- Chest discomfort
- Dyspnoea
- Respiration abnormal
- 3. Respiratory Event AESI (including respiratory symptoms or reactive airways)

The AESI of respiratory symptoms or reactive airways is defined as AEs whose PTs fall into any of the following categories:

- Asthma
- Bronchial hyperreactivity
- Bronchospasm
- Chest Discomfort
- Dyspnoea
- Respiration abnormal
- Wheezing

TE AESIs will be summarized using the Safety Set by:

- 1. Number and percentage of subjects by PT
- 2. Number and percentage of subjects by Maximum Severity
- 3. Descriptive summary of duration of events (days)
- 4. Descriptive summary of time-to-onset of the first event (days, relative to first dose date)
- 5. Number and percentage of subjects with exposure-adjusted number of events in 100PY for: (1) TEAEs Leading to Treatment Interruption; (2) TEAEs Leading to Treatment Discontinuation; (3) Serious TEAEs; (4) Related Serious TEAEs; and (5) TEAEs Leading to Death

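### The only hepatic AESI lists test-result terms alone, so a transaminase event recorded only as a diagnosis is left out of its summaries

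*SAP*

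**What the plan says.** SAP 10.6.1 decides membership of the Elevated Transaminases AESI by coded term alone: "The AESI of elevated transaminases is defined as AEs whose PTs fall into any of the following categories". Eleven PTs follow. Ten are an increased or abnormal form of ALT, AST, transaminases, liver function test or hepatic enzyme; the other is "Hypertransaminasaemia". No other AESI concerns the liver. On the status of the lists, the SAP says: "Three types of AESIs are proposed for Study 124; the Customized MedDRA Queries (CMQ) used may change before database lock".

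Each AESI gets five summaries: subjects by PT, maximum severity, event duration, time to first onset, and exposure-adjusted counts of events that led to interruption, discontinuation or death or were serious or related serious.

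Protocol 13.1.1.2 governs how an abnormal assessment becomes an adverse event: "When possible, a clinical diagnosis for the study assessment will be provided, rather than the abnormal test result alone". The fallback is: "In the absence of a diagnosis, the abnormal study assessment itself will be listed as the AE". Protocol 13.1.1.3 adds a merging rule: "When possible, a constellation of signs and/or symptoms will be identified as 1 overall event or diagnosis". When the liver-test interruption criteria in Protocol 11.4.3 are met, the protocol asks for a work-up: "A thorough investigation of potential causes should be conducted, and the subject should be followed closely for clinical progression".

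**The concern.** The two documents use different vocabularies for the same event. The SAP counts liver events by the name of the test, while the protocol steers sites towards the name of the disease. A transaminase rise that has been investigated and given a diagnosis may therefore carry a term that the AESI does not recognise.

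Safety is the primary endpoint, and the liver has its own monitoring and interruption rules in Protocol 11.4.3. One of those criteria combines a transaminase rise "in association with total bilirubin" elevation and/or clinical jaundice, yet neither bilirubin nor jaundice has a term in the list. A reader who takes the AESI table as the hepatic summary of the study could see too few affected children, and duration and onset figures drawn from only some of the events.

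**Working it through.** **1. What the list contains.** ALT, AST, transaminases, liver function test and hepatic enzyme each appear in two forms: 5 × 2 = 10 terms. Hypertransaminasaemia makes 11. It is worded as a condition but says no more than that transaminases are raised. Diagnoses of liver disease or injury: 0. Jaundice or bilirubin terms: 0.

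**2. How a transaminase event reaches the AESI, or does not.**

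| What the site records | Basis in Protocol 13.1.1.2 | Counted in the AESI? |
|---|---|---|
| Test result, no diagnosis available | The stated fallback | Yes, if coded to one of the 11 PTs |
| Diagnosis and test result | Not forbidden | Yes, through the test term |
| Diagnosis only | The preferred form, where possible | No |

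The gap is the third row. Protocol 11.4.3 itself mentions viral hepatitis as a possible cause of raised transaminases, so a diagnosis-only record is foreseeable.

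**3. What other planned outputs give for a diagnosis-only event.**

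| Information | Available elsewhere? |
|---|---|
| Incidence under its own PT | Yes: TEAE tables by SOC and PT, SAP 10.6.1 |
| Maximum severity, seriousness, relationship, interruption, discontinuation, death | Yes: separate TEAE tables by SOC and PT, SAP 10.6.1 |
| Individual case data | Yes: AE listings, SAP 10.6.1 |
| Measured ALT, AST and bilirubin peaks | Yes, if values qualify: threshold counts in SAP Appendix D and the liver-test listing in SAP 10.6.2, neither of which depends on AE coding |
| One incidence across liver-test and liver-diagnosis terms | No |
| Grouped duration and time to first onset | No: specified only for AESIs |

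**4. Size per subject.** The plan states no hepatic event rate, so it has no figure to reproduce. The one input it gives is N of about 50 (SAP 7.2). A subject whose only transaminase event is recorded only as a diagnosis changes AESI incidence by 1/N = 1/50 = 2.0 percentage points.

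**5. Illustration, with assumed counts.** Let k be the subjects with a transaminase-related event and m those recorded only under a diagnosis. Reported incidence is (k − m)/50. The exact (Clopper-Pearson) 95% intervals are added here and are not planned in the SAP.

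| k (assumed) | m = 0 | m = 1 | m = 3 |
|---|---|---|---|
| 3 | 6.0% (1.3 to 16.5) | 4.0% (0.5 to 13.7) | 0% (0 to 7.1) |
| 5 | 10.0% (3.3 to 21.8) | 8.0% (2.2 to 19.2) | 4.0% (0.5 to 13.7) |

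If each event is recorded only as a diagnosis with probability q, independently, the chance that at least one is left out is 1 − (1 − q)^k. For q = 5%, 20% and 40% this is 14%, 49% and 78% with k = 3, and 23%, 67% and 92% with k = 5. Neither k nor q is in the documents. The spread from 14% to 92% shows that the frequency cannot be judged from them.

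**The case against.** The list matches its name. It is an AESI of elevated transaminases, not of liver injury, so a broader grouping is an extra analysis and not the repair of an error. That stands, although no other hepatic AESI exists and the SAP gives no reason for stopping at test terms.

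The recording rule is also softer than a replacement rule. It applies where possible, and a diagnosis preferred to the test result alone leaves room for recording both. The merging rule in Protocol 13.1.1.3 speaks of signs and symptoms and does not mention laboratory tests. So the loss is conditional: it occurs when only the diagnosis is recorded.

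A reader might infer that liver events vanish from the safety analysis. They do not, as the third step of the working shows. With about 50 subjects, a serious liver diagnosis would be readable case by case.

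A reader might also infer that the two rules together remove the worst cases and leave the mild ones. The documents do not support this. Under Protocol 11.4.3, elevations without a convincing alternative cause are the ones that lead to discontinuation. Under Protocol 13.1.1.2, an elevation without a diagnosis is recorded as the test result. Unexplained cases that end treatment would therefore ordinarily be inside the AESI, while diagnosis-coded cases include those put down to another cause. An investigator could still record a drug-related liver injury as a diagnosis, but selection by severity is not shown.

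Finally, the SAP allows its queries to change before database lock. That permits a remedy but does not provide one: it names no terms to add and no rule for adding them, and in an open-label study a late change would be made with the data in view.

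**Conclusion.** The point holds as a gap in one set of summaries. A transaminase event recorded only as a diagnosis is left out of the AESI incidence, severity, duration, onset and action-taken summaries. Each subject affected lowers AESI incidence by about 2 percentage points. This assumes N of about 50 and that the child has no other event under a listed term. How many children would be affected is unknown.

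Severity, seriousness and action taken remain available by PT in the general tables. The net loss is a pooled hepatic incidence and grouped duration and time to onset. This is a cheap improvement to the plan, not a defect that undermines the safety analysis.

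**What to change.** In SAP 10.6.1:

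- Keep the 11-term Elevated Transaminases AESI as it is.
- Add a second, broader hepatic events AESI: those 11 terms plus PTs for hepatic diagnoses, jaundice and raised bilirubin. Print the full term list in the SAP; neither document supplies it, so it has to be drawn from the MedDRA version in use.
- Run the same five AESI summaries on the broader group.
- Fix both lists at SAP approval, before the data cut, in place of the open allowance for later change.

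This follows the pattern that the SAP already uses for respiratory events, where a three-term symptom AESI sits inside a seven-term AESI that adds asthma, bronchospasm, bronchial hyperreactivity and wheezing.

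The cost is SAP wording and one extra set of outputs on data already coded. The broader group may include liver events with a non-drug cause; the planned tables by relationship to study drug help in reading those. No visit, assessment or clinical rule changes.

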### 8.1.2 Exclusion Criteria

- 1. Prematurely discontinued LUM/IVA treatment in Study 122B.
- 2. History of any comorbidity or laboratory abnormality that, in the opinion of the investigator, might confound the results of the study or pose an additional risk in administering LUM/IVA to the subject (e.g., cirrhosis with portal hypertension).
- 3. History of drug intolerance or other serious reactions to LUM/IVA in Study 122B that would pose an additional risk to the subject in the opinion of investigator and which should be discussed with the Vertex medical monitor.
- 4. Subjects with a history of allergy or hypersensitivity to LUM/IVA.
- 5. Liver function test (LFT) abnormality meeting criteria for LUM/IVA treatment interruption at the completion of Study 122B, for which no convincing alternative etiology is identified.
- 6. QTc value at the completion of Study 122B that would pose an additional risk to the subject in the opinion of investigator, and should be discussed with the Vertex medical monitor (e.g., remained above the threshold value [>45 msec from baseline or >500 msec] on repeated measurement or was noted on 2 or more occasions with no identified alternative etiology for the increased QTc).
- 7. History of poor compliance with LUM/IVA and/or procedures in Study 122B as deemed by the investigator.
- 8. Participation in an investigational drug study (including studies investigating LUM and/or IVA) other than Study 122B. NOTE: Participation in a non-interventional study is permitted (including observational studies, registry studies, and studies requiring blood collections without administration of study drug).

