### **Duration of Dosing**

Subjects who receive LUM/IVA in Study 124 may receive treatment for up to 120 weeks (for Rollover Subjects: 24 weeks in Study 122B and 96 weeks in Study 124; for LUM/IVA-naïve Subjects: 96 weeks in Study 124), thus providing information on the long-term safety of LUM/IVA in subjects aged 1 year and older with CF, homozygous for *F508del*.

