#### 12.3.1 General Considerations

All individual subject data will be presented in data listings based on the 124 All Subjects Set.

Continuous variables will be summarized using the following descriptive summary statistics: number of subjects, mean, SD, SE, median, minimum value (min), and maximum value (max).

Categorical variables will be summarized using counts and percentages.

**Baseline value** will be defined as the most recent non-missing measurement (scheduled or unscheduled) collected on or before the first dose of LUM/IVA in Study 124.

For sweat chloride, values at each visit will be based on averaged measurements from left and right arms as specified in Section 11.2.1. For Rollover Subjects, baseline will be defined as the most recent non-missing measurement (scheduled or unscheduled) collected on or before the first dose of LUM/IVA in Study 124. For LUM/IVA-naïve Subjects, baseline will be defined as the average of the values at screening and the pretreatment measurement on Day 1 of Study 124. If only 1 pre-first dose measurement of sweat chloride is available, that measurement will be considered the baseline.

Change (Absolute Change) from baseline will be calculated as postbaseline value – baseline value.

**Current Study Period** starts from the first dose of study drug in Study 124 to the last day in Study 124.

The Treatment-emergent (TE) Period for the Current Study Period starts on or after the first dose date of study drug in Study 124 to 14 days (inclusive) after the last dose of study drug in Study 124 or up to the last day in Study 124, whichever occurs first.

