9 ANALYSIS PERIOD

The analysis periods are described below.

The **Treatment-emergent (TE) Period** will start on or after the first dose date of study drug in Study 124 to 18 days (inclusive) after the last dose date of study drug in Study 124 or up to the last day in Study 124, whichever occurs first.

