10.2.4 Study Drug Exposure

Duration of study drug exposure is defined as follows: last dose date in the TE Period – first dose date in the TE Period + 1 day, regardless of any dose interruptions. If the last dose date of study drug is missing and the ETT visit is available, use the ETT visit as the last dose date. Otherwise, if there is no ETT visit, the last known study participation date will be used for analysis purposes.

Duration of study drug exposure as well as number of sticks administered, defined as (total number of sticks dispensed) – (total number of sticks returned), will be summarized descriptively based on the Safety Set for the TE Period. Additionally, the total duration of treatment exposure, defined as the sum of the subject's duration of treatment exposure and expressed in patient-years (1 patient-year is defined as one patient with 48 weeks of treatment), will be provided.

Study drug administration data will be presented in individual subject data listings.

Duration of exposure will also be summarized as a categorical variable (>0 to \leq 8 weeks; >8 to \leq 24 weeks; >24 to \leq 48 weeks; >48 to \leq 72 weeks; >72 to \leq 96 weeks; >96 weeks).

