10.6.1 Adverse Events

AEs will be classified as pretreatment AEs, treatment-emergent adverse events (TEAEs), or post-treatment AEs, defined as follows:

Pretreatment AE: Any AE that started before the first dose date of study drug in Study 124.

TEAE: Any AE that worsened (either in severity or seriousness) or that was newly developed on or after the first dose date of study drug through the end of the TE Period.

Post-treatment AE: Any AE that increased in severity or was newly developed after the TE Period.

For AEs with missing or partial start dates, if there is no clear evidence that the AEs started before or after study treatment, the AEs will be classified as TEAEs.

Details for imputing missing or partial start dates of AEs are described in Appendix.

TEAE summaries will be presented using number and percentages of subjects for the TE Period based on the Safety Set.

An overview of the TEAE profile will be provided, including total number of TEAEs, with number and percentage of subjects and for the following categories: (1) Any TEAEs; (2) Grade 3/4 TEAEs; (3) TEAEs by Strongest Relationship to the Drug; (4) TEAEs by Maximum Severity; (5) TEAEs Leading to Treatment Interruption; (6) TEAEs Leading to Treatment Discontinuation; (7) Serious TEAEs; (8) Related Serious TEAEs; (9) TEAEs Leading to Death.

AE summary tables will be presented for TEAEs only and will include the following:

- All TEAEs
- Grades 3/4 TEAEs
- TEAEs by Strongest Relationship
- TEAEs by Maximum Severity
- Related TEAEs
- TEAEs Leading to Treatment Interruption
- TEAEs Leading to Treatment Discontinuation
- Serious TEAEs
- Related Serious TEAEs
- TEAEs Leading to Death
- Frequently Reported TEAEs (≥5% at the PT level)

These summaries will be presented by MedDRA SOC and PT using frequency counts and percentages (i.e., number and percentage of subjects with any event) and exposure-adjusted number of events in 100PY. When summarizing the number of events, a subject with multiple events within a category is counted multiple times in that category. When

summarizing the number and percentage of subjects with any event, subjects with multiple occurrences of the same AE or a continuing AE will be counted once, only the maximum severity level will be presented in the severity summaries, and only the strongest relationship level will be presented in the relationship summaries.

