	Week 84	589	[548, 631]
	Week 96	673	[632, 680]
	Follow-up Visit	687	Nominal Visit

Sweat chloride	Week 4	29	(1, 57]
 Fecal Sample 	Week 12	85	[58, 127]
1	Week 24	169	[128, 253]
	Week 48	337	[254, 505]
	Week 96	673	[506, 680]
	Follow-up Visit	687	Nominal Visit
Ophthalmological	Week 24	169	(1, 253]
Examination	Week 48	337	[254, 421]
	Week 72	505	[422, 589]
	Week 96	673	[590, 680]
	Follow-up Visit	687	Nominal Visit

The study days are based on the first dose in Study 124.

For Vital signs the Nominal Day 15 predose assessments will be mapped to Day 15.

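### AESI time-to-onset pools time since starting LUM/IVA (naïve subjects) with time since restarting it (Rollover Subjects), and no planned summary shows the up to 120 weeks of cumulative exposure

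*SAP*

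**What the plan says.** **Onset.** SAP 10.6.1 summarises treatment-emergent AESIs in five ways on the Safety Set. Item 4 is a "Descriptive summary of time-to-onset of the first event (days, relative to first dose date". It does not say which study's first dose, and no split between Rollover and LUM/IVA-naïve subjects is planned.

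**Origin of the clock.** The TE Period in SAP 9 "will start on or after the first dose date of study drug in Study 124". SAP Appendix A adds: "The study days are based on the first dose in Study 124". Protocol 12.3.1 is consistent: the Current Study Period "starts from the first dose of study drug in Study 124 to the last day in Study 124". Earlier events fall under "Pretreatment AE: Any AE that started before the first dose date of study drug in Study 124" (SAP 10.6.1), and the AE summary tables are for TEAEs only.

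**Exposure.** SAP 10.2.4 measures duration as last dose date minus "first dose date in the TE Period + 1 day, regardless of any dose interruptions", on the Safety Set for the TE Period. The top category is above 96 weeks.

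**Prior treatment of Rollover Subjects.** Protocol 8.1.1 requires that they completed the 24-week Treatment Period and the Safety Follow-up Visit of Study 122B. Protocol 8.1.2 excludes those who "Prematurely discontinued LUM/IVA treatment in Study 122B". Protocol 9.3.2 states: "Subjects who receive LUM/IVA in Study 124 may receive treatment for up to 120 weeks", split as 24 weeks in Study 122B and 96 in Study 124. SAP 7.1 repeats the split.

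**The concern.** The primary objective is long-term safety in children who were 12 to <24 months old when treatment began. For Rollover Subjects, treatment began in Study 122B. The same onset variable therefore means different things in the two cohorts:

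- LUM/IVA-naïve: days since first-ever LUM/IVA dose.
- Rollover: days since restarting after a completed 24-week treatment period and an off-drug interval.

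A reader would use onset of transaminase elevations and respiratory events to judge when after initiation they tend to appear. A pooled, unlabelled figure does not answer that. It does not describe time since restart either.

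Three features add to the problem. A Rollover Subject's first event in the table may be a later one, because a Study 122B AESI counts as pretreatment. The Rollover cohort is conditional on completing Study 122B, so early events may be under-represented in it. Detection also differs: in the first 16 weeks naïve subjects have liver tests at Day 15 and Weeks 4, 8, 12 and 16 (Protocol Table 3-2), Rollover Subjects only at Day 15 and Week 12 after Day 1 (Table 3-1).

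Separately, the longest exposure that the programme delivers in this age group, and which Protocol 9.3.2 links to its long-term safety information, would not be visible in any planned summary.

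**Working it through.** **1. The plan's own total.** 24 weeks (Study 122B) + 96 weeks (Study 124) = 120 weeks, or 120 × 7 = 840 days. This reproduces the figure in Protocol 9.3.2 and SAP 7.1.

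**2. What the exposure table can show.** Nominal Study 124 treatment is 96 × 7 = 672 days. The Week 96 analysis window closes at Day 680, so dosing up to the day before gives at most about (680 − 1)/7 = 97 weeks. The 120 weeks cannot appear.

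| Completing Rollover Subject | Weeks | Patient-years (48 weeks each) |
|---|---|---|
| Study 124 only | 96 | 96/48 = 2.0 |
| Study 122B + Study 124 | 120 | 120/48 = 2.5 |
| Omitted | 24 (24/120 = 20%) | 0.5 |

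If all of about 50 subjects completed, Study 124 exposure would be 50 × 2.0 = 100 patient-years. Cumulative exposure would be 100 + 0.5 × (number of Rollover Subjects), so between 100 and 125. The documents do not give the split.

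**3. Onset, first-ever AESI in Study 124.** Let g be the off-drug gap between the studies. Time from first-ever dose = SAP value + 168 + g, as elapsed time.

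- Event at Day 30: 30 + 168 = 198 days, before adding g.
- The documents do not give g. If it is 14 days (assumption), the shift is 168 + 14 = 182 days.
- If g is 10 to 18 days and the Study 122B Week 24 visit falls within ±7 days (both assumptions), the shift runs from 168 − 7 + 10 = 171 to 168 + 7 + 18 = 193 days.
- A Study 124 Day 1 later than the Study 122B Safety Follow-up Visit, which Protocol 9.1 allows, lengthens g.
- For LUM/IVA-naïve subjects the shift is 0.

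**4. Onset, earlier AESI in Study 122B.** Let D = (day of first-ever AESI, counted from first Study 122B dose) − (SAP value). Illustrative cases:

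| First AESI in Study 122B | First AESI in Study 124 (SAP value) | D |
|---|---|---|
| Day 30 | Day 60 | −30 |
| Day 100 | Day 20 | +80 |
| Day 15 | Day 300 | −285 |

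So 168 days is not a general minimum, and adding a constant would not repair the variable.

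**5. Effect on a pooled mean.** Suppose a share s of the subjects in the onset table are Rollover Subjects of the kind in step 3. On the initiation clock the pooled mean would be later by s × 168 days, ignoring g: 33.6 days at s = 0.2, 84 at s = 0.5 and 134.4 at s = 0.8. The documents give no value for s, so this shows a range and is not an estimate.

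**The case against.** **The clock is deliberate.** Protocol 12.3.1 defines the Current Study Period and TE Period from the first Study 124 dose, and the SAP follows it. The protocol's summary of changes shows that the pretreatment AE definition was revised with Study 122 events in mind. Time since restart is also a meaningful quantity: Protocol 9.5 describes an initial transient decline in lung function on dosing. This stands. A reader might infer that Rollover onset times are simply wrong, or wrong by at least 168 days. The documents do not support that. Days since first Study 124 dose is a defined within-study measure, and the 168-day shift applies only to subjects whose first-ever AESI falls in Study 124. Because Protocol 8.1.1 admits subjects with Study 122B interruptions, it is elapsed time and not necessarily time on drug.

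**Study 122B events are not lost.** SAP 10.6.1 lists pretreatment AEs, and an event that worsens after the first Study 124 dose becomes a TEAE. This stands. They are absent from the summaries, not from the report, and the label for them is only terminology.

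**Selection is partial.** Protocol 8.1.2 excludes only liver test abnormalities that meet interruption criteria at Study 122B completion without a convincing alternative cause, and only those reactions that the investigator judges an added risk. Protocol 8.1.1 allows some subjects who resumed after transaminase elevations. This also stands, although everyone who stopped treatment early in Study 122B is excluded.

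**The 120 weeks is a permitted maximum, and the SAP is for Study 124.** That is correct. Cumulative exposure may be reported elsewhere, but neither document says so.

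**The summaries are descriptive**, with about 50 subjects and no hypothesis testing. This limits the stakes.

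None of these points answers the pooling of two time origins under one unlabelled heading.

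**Conclusion.** The point holds as one of interpretability. Followed exactly, the plan gives one onset summary that combines time since initiation with time since restart, in which a Rollover Subject's first event may not be the first on LUM/IVA. For a Rollover Subject whose first-ever AESI falls in Study 124, the two clocks differ by nominally 168 days plus an unstated off-drug gap. With an earlier Study 122B AESI the difference is smaller and can take either sign. For naïve subjects it is zero. The net effect on the pooled figure cannot be stated, because neither the cohort split nor the distribution of events is given.

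For exposure, 24 of 120 weeks (20%) of a completing Rollover Subject's treatment is in no planned summary.

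This rests on reading item 4's unqualified first dose date as the Study 124 date, which follows from the TE Period and study-day definitions. It does not show that the within-study clock is an error or that Study 122B events go unreported. The change is worth making because safety is the primary objective and the cost is low.

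**What to change.** **SAP 10.6.1, item 4**
- State that the clock is the first dose in Study 124.
- Present onset separately for LUM/IVA-naïve subjects (labelled time since initiation) and Rollover Subjects (labelled time since restart), with no pooled figure.
- For each Rollover Subject with an AESI, also list time from first Study 122B dose and any earlier Study 122B AESI. Note that this cohort is conditional on completing Study 122B.
- Do not pool onset from the first Study 122B dose with the naïve subjects. Children who stopped in Study 122B because of an AESI would be missing, so the result would carry that selection.

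**SAP 10.2.4**
- Present Study 124 exposure by cohort.
- For Rollover Subjects, add cumulative LUM/IVA exposure (Study 122B duration + Study 124 duration, excluding the off-drug gap), with categories reaching 120 weeks.
- Keep Study 124 exposure as the denominator for the event rates per 100 patient-years, since their numerators are Study 124 events.
- If the sponsor intends to report cumulative exposure elsewhere, a sentence saying where would replace the added summary.

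**Cost.** A short SAP amendment, a few extra table columns, one listing, and a merge of Study 122B dose dates and AESI records. Study 124 already uses Study 122B visit assessments and medical history; the AE merge is an additional step. The cohorts will be small, so the separate onset summaries will be imprecise.
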